#### II. Exclusion

A. Subjects will be excluded if they are unable to provide informed consent, are currently pregnant, have a positive screening test (listed above) or have a known medical history of any of the following:

1. Psychiatric conditions
2. Skin disorders or open wounds precluding skin contact
3. Fasciitis or fascial tears
4. Myositis
5. Neurological symptoms such as numbness, tingling, weakness in upper extremities
6. Neoplasia
7. Bone fracture, osteomyelitis, or osteoporosis
8. Coagulation problem
9. Deep vein thrombosis
10. Adrenal diseases/syndromes
11. Acute upper or lower respiratory infection
12. Immunosuppressive syndromes
13. Radiation or chemotherapy within the past 3 years
14. Lupus
15. Osteopenia
16. Congestive heart failure
17. BMI greater than 30

18. Any other autoimmune disease not stated above
  19. Medication changes within the last 4 weeks
  20. Asthma exacerbations within the last 4 weeks
  21. Immunosuppressive therapy as a consequence of organ transplantation
  22. Immunosuppressive therapy as a consequence of allogeneic cellular transplantations or bone marrow stem cell transplantation
  23. Other conditions often requiring immunosuppressive therapy
  24. Anticoagulant therapy
  25. Known sensitivity to the carotid sinus reflex
  26. Advanced carotid disease
  27. Down syndrome
- B. Subjects will be screened for eligibility based on the inclusion and exclusion criteria described above at the point of subject consent. No protected health information will be collected from subjects who are not eligible to participate in the study.
- C. If subjects develop any of the above issues during the course of the study, they will be removed from the study without penalty and will still receive compensation.
- D. All female patients will be screened in the selection process by self-report as to whether or not they are pregnant. Under any suspicion of pregnancy, the participant will be ineligible for participation.
- III. Definition of treatment failure or subject removal criteria
- A. Subjects who do not adhere to the full treatment regimen will be removed from the study.
- B. Subjects who experience any adverse effects from treatment, as determined by a licensed osteopathic physician, will be immediately removed from the study. However, we do not anticipate any adverse effects during the study. Last year we have successfully utilized OMT and the BEMER therapy without any adverse effects in a prior study on low back pain.

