### **Review of Literature:**

Neck pain is estimated to have a prevalence of 30% annually and perhaps, affect 70% of patients at some point in their life [1, 2]. Neck pain has become a very important public health problem, and social issue due to its high prevalence, unsatisfactory treatment options, large medical burden, and reduction in quality of life [11]. In fact, neck pain ranks fourth worldwide as a cause of Years Lived with Disability [12]. Many complaints of acute or chronic neck pain are musculoskeletal in nature and present with significant muscular tension in the neck, which may restrict blood flow.

Neck pain can result from a variety of etiologies, including postural, neurological and mechanical causes such as muscle strains, joint damage, and nerve compression [2]. Several treatment options are currently available for the various causes of neck pain such as nonsteroidal anti-inflammatory and steroid pharmacotherapy, surgery, and an array of more conservative treatments including Osteopathic Manipulative Treatment (OMT). Palpation of the posterior and anterior neck muscles for tissue texture changes and tender points can assist in the diagnosis of cervical dysfunctions [13]. The upper cervical and upper thoracic regions can contribute to temporomandibular joint (TMJ) dysfunction through the continuity of fascia. The utilization of OMT on these somatic dysfunctions can be greatly beneficial to these patients. Dysfunction of the occiput and atlas is associated with the temporal bone and these tender points located between the ramus of the mandible and mastoid process can be effectively treated with counterstrain, which is an osteopathic manipulative technique [13].

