  - b) Each subject in the OMT groups (i.e. OMT and OMT+BEMER) will receive treatment 3 times per week for a period of 3 weeks. As previously mentioned, subjects in the BEMER groups (i.e. BEMER and OMT+BEMER) will receive treatment 5 times per week for a period of 3 weeks. Finally, subjects in the Placebo group will receive the combined light touch and BEMER sham treatments at same intervals as the corresponding experimental groups. OMT, BEMER, and placebo treatments will be performed by osteopathic medical students who have completed additional training given by a licensed osteopathic physician, to ensure uniform technique. All treatments will be performed during the span of three consecutive weeks.
  - c) Subjects will complete brief questionnaires regarding neck pain and quality of life before the beginning of study and will complete the same questionnaires following the completion of the three week treatment (Appendices C, E, F).

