## **Risks and Benefits**

- I. Risks
- A. Anticipated medical risks
1. After OMT, muscle tenderness and generalized discomfort may be noted 24-48 hours after treatment in a small number of patients.
  2. There is little empirical data about the “hazards” to patients of student-performed procedures. Further, this study does not employ any inherently forceful techniques (such as high velocity low amplitude HVLA).
  3. There are no anticipated adverse effects associated with BEMER therapy. In addition, we have already utilized the BEMER therapy in a prior study on low back pain. No adverse effects were noted.
- B. Steps taken to minimize the risks
1. All Osteopathic Medical students performing osteopathic manipulation will receive additional special training by a licensed osteopathic physician, member of the LECOM-Bradenton OMM Department, and will disclose their true identity to the subjects to avoid any misconceptions that they are licensed physicians. Student-treaters will be critiqued by a physician until they are approved to perform OMT on the subjects.

2. A licensed osteopathic physician will be in the vicinity of the treatment location at all times a treatment is being given. [name] will be in the building and, if not in the treatment room, will be available by phone and/or text message at all times during treatments and will respond immediately to matters involving the study participants and/or treatments.
  3. All treatments will be performed by osteopathic medical students. [name] will provide students additional training on OMT and placebo treatments, and [name], a BEMER representative, will provide additional training on BEMER treatments.
  4. There are no funds designated to compensate subjects for injury. The principal investigator will work with injured subjects to provide them with further information to the best of his ability.
- C. Plan for reporting adverse events
1. All serious or unanticipated adverse events will be reported to the LECOM IRB promptly.
  2. All protocol amendments will be submitted to the IRB for approval, with the exception of changes that must be made in order to eliminate any imminent risk of harm to subjects or to others. In this circumstance, the investigator will act to eliminate the immediate risk but must subsequently submit an appropriate protocol amendment and await approval before proceeding with the revised protocol.
- II. Benefits
- A. Description of probable benefits

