### **Appendix C: Visual Analog Scale**

The Visual Analog Scale (VAS) is a 100-millimeter line with “no pain” on one end and “pain as bad as it can be” at the other end. This scale is a very simple form of assessment. Patients are expected to mark on the line the amount of pain they are experiencing.

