#### Section 1: Pain Intensity

- = I have no pain at the moment
- = The pain is very mild at the moment
- = The pain is moderate at the moment
- = The pain is fairly severe at the moment
- = The pain is very severe at the moment
- = The pain is the worst imaginable at the moment

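### Subjects' own pain-medicine use is not recorded, and the plan does not say whether a change in it during the study leads to removal; either way the VAS comparison could be distorted without anyone being able to check

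*Combined protocol and SAP*

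**What the plan says.** **Data collected.** Methodology II.A.3(c) states: "Subjects will complete brief questionnaires regarding neck pain and quality of life before the beginning of study". The same forms are repeated after the three weeks, and the paragraph cites Appendices C, E and F only (VAS, NDI, SF-12). Section III.A lists these three instruments as the outcome.

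**What the pain items ask.** Appendix C has subjects "mark on the line the amount of pain they are experiencing". NDI Section 1 is also about the present, with options such as "The pain is very mild at the moment".

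**Medicines as treatment.** The Review of Literature says: "Several treatment options are currently available for the various causes of neck pain such as nonsteroidal anti-inflammatory and steroid pharmacotherapy". Methodology IV says that the trial uses no drugs. That describes the study interventions and neither restricts nor records what subjects take on their own.

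**Rules that could touch pain medicine.** Exclusion item 19 reads "Medication changes within the last 4 weeks", with no drug class and no definition of a change. Paragraph C of the same section adds: "If subjects develop any of the above issues during the course of the study, they will be removed from the study without penalty". Paragraph III.B separately removes subjects judged by the physician to have an adverse effect of treatment.

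**Expected soreness.** Risks and Benefits I.A.1 says that after OMT "muscle tenderness and generalized discomfort may be noted 24-48 hours after treatment in a small number of patients". Item I.A.3 anticipates no adverse effects from BEMER.

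**Analysis.** Section III.A.2 plans paired t-tests within each arm (about 10 subjects) and a one-way ANOVA across the four arms. It has no medication term and no rule for the data of removed subjects.

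**The concern.** An analgesic taken shortly before scoring can lower a momentary pain score whatever the allocated treatment did. The plan names drugs as a competing treatment for the same complaint, yet measures their use at no point.

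The one exclusion item that could reach pain medicine leaves two readings open.

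- **Applied during the study.** A subject who starts an analgesic because the neck is worse, or stops one because it is better, has changed medication and is removed. Loss then depends on the outcome itself.
- **Not applied, or the change goes unnoticed.** The subject stays and is scored with the drug on board. If use after randomisation differs between arms, part of the arm difference belongs to the drug.

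The expected soreness after OMT is one route by which use could differ between arms. At stake is whether the week-3 VAS difference, and to a lesser degree the NDI difference, can be read as a treatment effect. Use that was not recorded at the time cannot be reliably rebuilt later.

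**Working it through.** **1. The plan's own figure.** Four arms at about 10 each give 4 x 10 = 40, which matches the 40 subjects in the cost estimate. The plan gives no SD, effect size, alpha or power, so the N of about 10 cannot be derived further. It is taken as given below.

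**2. Reach of item 19 if it applies after entry.** The look-back is four weeks and the study lasts three. Any change made after entry therefore still falls inside the look-back at the final visit, and on the literal reading every start or stop triggers removal.

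**3. Users kept.** Bias in the arm difference = (difference between arms in the proportion medicated at scoring) x (analgesic effect on the VAS). Both inputs are assumptions.

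| Difference in use | Effect 10 mm | Effect 20 mm |
|---|---|---|
| 0 points | 0 mm | 0 mm |
| 10 points | 1 mm | 2 mm |
| 20 points | 2 mm | 4 mm |
| 30 points | 3 mm | 6 mm |

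For scale, assume an SD of 20 mm. The standard error of an arm difference is 20 x sqrt(2/10) = 8.9 mm, so 0-6 mm is 0 to 0.7 standard errors. With 10 per arm, 30 points means three more medicated subjects in one arm than in the other.

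**4. Users removed.** Assume that VAS change is normal with SD 20 mm, mean -10 mm under control and -20 mm under active treatment (a true difference of 10 mm). Suppose subjects whose change is at or above a threshold c start an analgesic and are removed. The completer mean is m - 20 x phi(z)/Phi(z), with z = (c - m)/20.

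| c | Control removed | Active removed | Control completers | Active completers | Apparent difference |
|---|---|---|---|---|---|
| 0 mm | 31% | 16% | -20.2 mm | -25.8 mm | 5.6 mm |
| +10 mm | 16% | 7% | -15.8 mm | -22.8 mm | 7.0 mm |
| +20 mm | 7% | 2% | -12.8 mm | -21.1 mm | 8.3 mm |

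First row: control z = 0.5, so -10 - 20 x 0.352/0.691 = -20.2; active z = 1, so -20 - 20 x 0.242/0.841 = -25.8.

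Two things follow. The between-arm difference shrinks from 10 mm, and the control arm's own improvement is overstated, which inflates its paired t-test. If there is no true difference and removal works alike in both arms, the between-arm bias is zero, but the within-arm overstatement remains. The model covers only removal after worsening. Removing subjects who stop a drug because they improved acts in the opposite direction.

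**5. NDI.** Only Section 1 asks about pain at that moment. It carries 5 of 50 points, or 10% of the score, so recent analgesia has less direct leverage than on the VAS. No NDI bias is computed.

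**The case against.** Several stronger readings are tempting, and the documents do not support them.

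- **That item 19 is the plan's only medicine rule.** It is not. Item 24 excludes "Anticoagulant therapy", and items 13, 21 and 22 concern other therapies. Item 19 is the only one that could reach pain medicine.
- **That the arms do differ in analgesic use.** Nothing shows this. Randomisation balances baseline use in expectation, though imperfectly at about 10 per arm, and equal use gives zero bias. The risk lies in use after randomisation.
- **That soreness gives OMT subjects a reason to medicate for much of the week.** Three sessions a week at 24-48 hours each would be 72-144 of 168 hours (43-86%). But the plan expects soreness in only a few patients, and its hours may say when soreness is noticed rather than how long it lasts. This figure does not enter the bias calculation.
- **That the bias favours OMT.** Soreness may itself raise the VAS, and a drug taken for it may only cancel that rise. More use under placebo would shrink the apparent benefit. Sore subjects might also be removed under III.B.

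Two further objections carry weight. If the question is the effect of allocation whatever else subjects take, analgesic use is part of the outcome and not a bias; but the plan does not state that question, and use would still need reporting for the result to be interpreted. Also, the assumed bias is smaller than one standard error, and the selection problem belongs in part to the removal rules generally. Both limit the weight of the point without removing it.

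Finally, the consent form and some appendix text were not available for review, and the contents of the data collection logs are not described. The finding is therefore that no available text provides for the record. The questionnaire paragraph does cite only Appendices C, E and F.

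**Conclusion.** The point stands as a cheap improvement, not as a demonstrated bias. The available text has no record of pain-medicine use, and it does not settle whether item 19 operates after entry or which medicines it covers. Following the plan therefore either removes subjects for a reason tied to their pain or leaves a competing treatment unmeasured.

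If users stay, the assumed inputs give 0-6 mm on the VAS, in either direction, against a standard error of about 9 mm. If subjects who worsen are removed, the assumed model shows a true 10 mm difference as 5.6-8.3 mm and a control change of -10 mm as -12.8 to -20.2 mm. All of these sizes rest on the assumed analgesic effect, use rates, SD, mean changes and removal thresholds; the documents give none of them. That analgesic use is unequal, or that it favours a particular arm, is something a reader might infer but the plan does not establish.

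**What to change.** 1. **Record use.** On the pre and post questionnaires, in all arms, ask which pain medicine was taken in the previous 24 hours and when. On the post form, also ask about use over the three weeks. Keep the recall schedule the same in every arm: logging by visit would give OMT-only subjects 9 reporting points and the BEMER arms 15.
2. **Reconcile the rules.** The sponsor should reconcile item 19, paragraph C of the Exclusion section, paragraph III.B and Risks and Benefits I.A.1, and state whether item 19 applies after entry and to which medicines. Which rule is right is a clinical decision that this review does not make.
3. **Keep the outcome data.** Whatever that rule is, seek week-3 scores from every randomised subject, including those removed, and include them in the between-arm comparison.
4. **Report.** Show analgesic use by arm beside the VAS and NDI results as a descriptive finding. Label any sensitivity analysis that accounts for use as exploratory, because use arises after randomisation, treatment may affect it, and there are only about 10 subjects per arm.

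The cost is a few questions on existing forms, clarified wording in the removal rules, contact with removed subjects for one final set of scores, and slightly more data entry.

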### III. Analysis

#### A. Study Statistics

1. Primary outcome variable
  - a) Questionnaire ratings before and after treatments
    - (1) Neck Disability Index (Appendix E) [28-31]
    - (2) SF-12 Health Survey (Appendix F) [32]
    - (3) Visual Pain Analog (Appendix C) [33]
2. Statistical plan including sample size justification and interim data analysis
  - a) Paired T-tests (N~10 subjects) to investigate the changes in neck pain after each treatment protocol.
  - b) One-Way ANOVA to investigate any statistically significant differences between the means of each of the 4 experimental groups.
3. Early stopping rules

- a) Any adverse effect, as determined by the attending licensed osteopathic physician. No adverse effects are anticipated.
- B. Blinding
  - 1. All outcome analyses will be performed in a blinded fashion. Subject survey and corresponding data will be de-identified and analyzed retrospectively by investigators with no exposure to the treatment sessions. Doing so will eliminate bias associated with investigator self-interest and ensure subject anonymity.

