## **Payment and Costs**

### **I. Payment**

A. All subjects will receive a compensation of \$50 the form of a gift card for a local eating/shopping establishment at the time of completion of the study.

B. Subjects who cannot complete the protocol due to adverse events will still be compensated.

C. Subjects who are noncompliant with protocol will not receive compensation.

D. No fees for participation.

E. No penalties for participation or non-completion.

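### Randomised participants are removed for non-adherence, adverse effects or new exclusion issues, with no week-3 scores after removal and no analysis set, so the plan as written compares completers

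*Combined protocol and SAP*

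**What the plan says.** Three rules under Research Participants take people out of the study after randomisation:

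- III.A, adherence: "Subjects who do not adhere to the full treatment regimen will be removed from the study". No tolerance is given.
- III.B, adverse effects: "Subjects who experience any adverse effects from treatment, as determined by a licensed osteopathic physician, will be immediately removed from the study".
- II.C, for anyone who develops a listed exclusion issue on study: "they will be removed from the study without penalty and will still receive compensation".

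On outcomes, Methodology II.A.3.c has participants complete the questionnaires at baseline and says that they "will complete the same questionnaires following the completion of the three week treatment". No other post-baseline assessment is described.

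On analysis, Methodology III.A.2 lists two items: "Paired T-tests (N~10 subjects) to investigate the changes in neck pain after each treatment protocol" and "One-Way ANOVA to investigate any statistically significant differences between the means of each of the 4 experimental groups". It names no analysis set, no missing-data rule and no allowance for dropout.

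On payment, Payment and Costs I.B says: "Subjects who cannot complete the protocol due to adverse events will still be compensated". I.C withholds payment from the noncompliant, while I.E says that non-completion carries no penalty.

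**The concern.** The rules end participation in the study, not only treatment. A removed participant has no scheduled week-3 score, and a paired test or an ANOVA of change needs that score. The analysed set is then those who finished, and randomisation no longer protects the comparison if finishing is related to outcome.

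No rule removes anyone for poor response, but some routes could track neck status. The exclusion list applied by II.C includes upper-extremity neurological symptoms and medication changes. Risks and Benefits I.A.1 anticipates tenderness and discomfort after OMT in a few participants and does not say whether these count as adverse effects.

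Exposure to the adherence rule also differs by arm: 9 OMT treatments, 15 BEMER treatments, and both in the combined arm. Loss may therefore differ by arm. Noncompliant participants go unpaid, which gives them less reason to return a questionnaire.

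Separately, each removal shrinks arms planned at about 10.

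**Working it through.** **What can be reproduced.** Four arms of about 10 give 40, which matches the budget (40 × $50 = $2,000). The figure of about 10 per arm cannot be derived, because no alpha, power, effect size, SD or dropout rate is stated. Everything below rests on assumptions, with two-sided alpha 0.05 and 80% power.

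**1. Loss under III.A.** Inputs from Methodology II.A.1: OMT 3 × 3 = 9 sessions; BEMER 5 × 3 = 15; combined 15 visits if both are given together, or 9 + 15 = 24 treatments if counted separately. The placebo schedule is not explicit, so it is taken as 15 or 24 too. Assume independent misses with probability p per session and that any miss means removal. Completion is c = (1 − p)^k.

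| p | k = 9 | k = 15 | k = 24 | N left: 10(c9 + 3·c15) | N left: 10(c9 + c15 + 2·c24) |
|---|---|---|---|---|---|
| 1% | 0.914 | 0.860 | 0.786 | 34.9 | 33.4 |
| 3% | 0.760 | 0.633 | 0.481 | 26.6 | 23.6 |
| 5% | 0.630 | 0.463 | 0.292 | 20.2 | 16.8 |

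**2. Detectable effect.** For a four-group ANOVA (noncentral F with 3 and N − 4 degrees of freedom, noncentrality N·f²), the detectable f is 0.551 at N = 40; 0.595 at 35; 0.615 at 33; 0.692 at 27; 0.744 at 24; 0.835 at 20; 0.932 at 17. The detectable pairwise difference is 1.32 SD with 10 per arm, 1.51 SD with 8 and 1.80 SD with 6.

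**3. Shift of a completer mean.** Let removal depend on a normal variable that correlates r = 0.3 with change. The completer mean then moves by r·φ(z)/c, with z = Φ⁻¹(1 − c).

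| p | k = 9 | k = 15 | k = 24 | 15 v 9 | 24 v 9 |
|---|---|---|---|---|---|
| 1% | 0.052 | 0.078 | 0.111 | 0.026 | 0.060 |
| 3% | 0.123 | 0.178 | 0.248 | 0.056 | 0.126 |
| 5% | 0.180 | 0.257 | 0.353 | 0.078 | 0.173 |

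All values are in SD of change. The last two columns are the bias between OMT and an arm with 15 or 24 sessions. Combined versus placebo is zero here, because both are given the same count and the same r.

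**4. Error rates.** Simulation with no true change, 10 per arm, 400,000 runs, and 1 or 2 removed from one arm at r = 0.3:

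- Mean shift: 0.05 or 0.095 SD.
- False improvement in that arm's paired test: from 2.5% to about 3.5% or 4.4%.
- Two-sample false positives: from 5.0% to about 5.2% or 5.5%.
- Four-arm ANOVA on completers, with the losses of step 1 and at least 2 completers per arm: 5.0% to 5.4%.

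A ceiling that no section supports is removal of exactly the worst 1 or 2 of 10. The shift is then 0.17 or 0.32 SD, and false improvement in the paired test about 9% or 19%.

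**5. If loss is uneven across arms.** With 40% lost in one arm and 10% in the others, a simulation of 4,000 runs gives an ANOVA false-positive rate of about 5.4% at r = 0.3, 6.1% at 0.5 and 9.2% at 0.8.

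**The case against.** The strongest reply is that the modelled between-arm bias is small: at most 0.17 SD at r = 0.3, against a detectable difference of 1.32 SD, with ANOVA error near 5%. That stands for the model in steps 1 to 4. The model covers III.A only and uses one correlation for all arms, so it does not bound what the other two removal routes could do.

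Second, the restriction to completers is inferred from silence, since nothing forbids collecting or using scores after removal. This is correct. But no section provides for such scores, and a plan followed literally will not obtain them.

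Third, treating any missed session as removal is the harshest reading. Recruitment email sessions are scheduled individually, and make-up sessions are neither offered nor excluded, so true loss may be lower. The 17-20 of 40 scenario depends on that reading.

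Fourth, adverse-effect removals may be rare, since III.B reports of earlier use: "Last year we have successfully utilized OMT and the BEMER therapy without any adverse effects in a prior study on low back pain". No number of participants is given for that study, so it sets no upper limit on the rate.

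These replies limit the size of the problem. They do not supply the missing scores or an analysis set.

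**Conclusion.** The concern holds and should be fixed before enrolment. Removal after randomisation, one post-treatment assessment tied to finishing treatment, and the absence of an analysis set together produce a completers-only comparison. The rate of loss and the direction of any bias cannot be determined from the documents.

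Under the assumptions shown, the clearest costs are lost participants and inflated false improvement in the within-arm paired tests, which the plan lists first. Between-arm bias is modest unless removal is strongly related to outcome and uneven across arms. The main reason to act is that no later analysis can replace scores that were never collected. Keeping everyone preserves about 10 per arm; it does not make the trial well powered.

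**What to change.** Leave every clinical rule on stopping treatment, and the physician's decisions, as they are. Separate them from outcome collection with two additions.

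- **Research Participants, III:** *Removal does not end outcome collection. Every randomised participant who has not withdrawn consent is asked to complete the NDI, VAS and SF-12 at week 3, counted from the first scheduled session.*
- **Methodology, III.A.2:** *The main analysis includes all randomised participants with a week-3 score, in the arm assigned. Missing scores and removals are reported by arm and reason. Full adherers form a secondary per-protocol set. If scores are missing, a sensitivity analysis varies the assumed change for those participants over a prespecified range that includes worsening, separately by arm.*

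The main set still omits anyone without a week-3 score, so the sensitivity range should be fixed in advance. One imputed value is not enough. Suppose both arms truly improve by 1 SD and 2 of 10 placebo scores are missing. Assigning those two a change of d gives a spurious active advantage of 1 − (0.8 × 1 + 0.2 × d) = 0.2 × (1 − d), which is 0, 0.20 or 0.40 SD for d = +1, 0 or −1.

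The cost is an IRB amendment, a check that the consent form allows follow-up after removal, and three existing questionnaires for those removed. Including partial adherers may dilute the estimated effect slightly. Paying for the final questionnaire is optional, at up to $50 per non-adherer; the $2,000 budget covers it if 40 means participants randomised. Payment on completion may also encourage adherence, so changing it is a trade-off. Payment and Costs I.C and I.E should be reconciled in any case.

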H. OMT, BEMER, and placebo will be performed by osteopathic medical students who have completed additional training given by a licensed osteopathic physician to ensure uniform technique. A licensed osteopathic physician will be in the vicinity of the treatment location at all times while treatments are being given.

I. All data collection logs will be de-identified of personal information and only contain the randomized participant ID number linking the participant to the data collected.

J. The identifying information will be maintained by the principal investigator in a locked cabinet, which they alone have access to.

II. Study Procedures and Timeline

A. Study duration

1. The study duration is three weeks. The subjects will be required to have either OMT, BEMER, OMT+BEMER, or Placebo treatments during the course of the study. Each subject in the OMT groups (i.e. OMT and OMT+BEMER) will receive treatment 3 times per week for a period of 3 weeks. Subjects in the BEMER groups (i.e. BEMER and OMT+BEMER) will receive treatment 5 times per week for a period of 3 weeks. Finally, subjects in the Placebo group will receive the combined light touch and BEMER sham treatments at same intervals as the corresponding experimental groups. OMT, BEMER, and placebo treatments will be performed by osteopathic medical students who have completed additional training given by a licensed osteopathic physician, to ensure uniform technique.
2. Recruitment:
  - a) LECOM-Bradenton faculty, staff, osteopathic medical, dental, pharmacy, and master's students will be informed via email of the opportunity to participate in the research study and will be given contact information to confirm eligibility with a study coordinator (Appendix A).
3. Experimental Sessions
  - a) Following written consent (Appendix B), subjects will be given a randomized study ID number. They will be randomized into their treatment group.

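### A subject with any adverse effect is removed from the study rather than only from treatment, and no post-treatment outcome is planned for that subject

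*Combined protocol and SAP*

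**What the plan says.** Three clauses under Research Participants take subjects out after randomisation.

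- Section III.B, on adverse effects: "Subjects who experience any adverse effects from treatment, as determined by a licensed osteopathic physician, will be immediately removed from the study". It sets no severity threshold, and it names the study rather than the treatment.
- Section III.A, on adherence: "Subjects who do not adhere to the full treatment regimen will be removed from the study". It makes no exception for treatment that was stopped for an adverse effect.
- Section II.C, on listed exclusion conditions: "If subjects develop any of the above issues during the course of the study, they will be removed from the study without penalty".

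Outcomes are collected twice. Subjects fill in the questionnaires before the study and, under Methodology II.A.3 (Experimental Sessions), "will complete the same questionnaires following the completion of the three week treatment". The recruitment email (Appendix A) repeats this schedule. There is no early-termination assessment, no follow-up of removed subjects, no defined analysis set and no missing-data rule. For subjects who cannot finish because of adverse events, Payment and Costs I.B keeps the payment and mentions no outcome visit.

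The analysis (Methodology III.A.2) is a paired comparison within each arm, "Paired T-tests (N~10 subjects) to investigate the changes in neck pain after each treatment protocol", and a one-way ANOVA across the four arms.

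**The concern.** Removal under III.B depends on what the assigned treatment did to the subject. If that subject's final questionnaires are never collected, the arms that are analysed need no longer be the arms that were randomised. All three outcomes are self-reported pain, disability or quality of life, and an adverse effect could plausibly move any of them. Outcomes not collected at week 3 cannot be recovered by any later analysis. With arms of about 10, a single loss is visible.

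**Working it through.** **Following one subject through the text.** Suppose the physician determines an adverse effect in week 2.

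1. III.B removes the subject from the study at once.
2. The only post-baseline assessment comes after the three weeks, so none is planned for this subject.
3. A paired t-test needs both values, and an ANOVA on post-treatment or change scores needs the later one. The subject enters neither.
4. Rewording III.B alone would not help. A subject whose treatment stops in week 2 has not had the full regimen, so III.A removes the same person. If the event was arm numbness, tingling or weakness (item 5 of the exclusion list), II.C would do so too.

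**Arm size.** The plan's figure is about 10, read as per arm. This agrees with the budget: 4 × 10 = 40 subjects and 40 × $50 = $2,000 (Payment and Costs II.A.2). No alpha, power, effect size or SD is given, so the figure cannot be reproduced further. One loss is 1/10 = 10% of an arm.

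**How large the effect could be.** The documents give no adverse-effect rate, so everything here is assumed. Take the one case in which losses would concentrate: post-OMT soreness (Risks and Benefits I.A.1) is counted as an adverse effect. The two OMT arms hold 2 × 10 = 20 subjects. Let p be the removal probability, and let d be the gap between removed and retained subjects in SD units of the analysed score, taken as 0 to 1 in either direction.

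- Expected removals = 20p
- Chance of at least one removal = 1 − (1 − p)^20
- Average shift in an OMT-arm mean = p × d

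| Assumed p | Expected removals | Chance of at least one | Shift at d = 0 | Shift at d = ±1 |
|---|---|---|---|---|
| 0% | 0 | 0% | 0 | 0 |
| 2% | 0.4 | 33% | 0 | ±0.02 SD |
| 5% | 1 | 64% | 0 | ±0.05 SD |
| 10% | 2 | 88% | 0 | ±0.10 SD |

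The standard error of a difference between two arms of 10 is √(1/10 + 1/10) = 0.447 SD. The shift is then at most 0.05/0.447 = 11% of it at rates up to 5%, and 0.10/0.447 = 22% when both assumptions are at their extremes.

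On the 100 mm VAS, with one of ten removed and an assumed 20 mm gap, the arm's mean change is off by 20 × 1/10 = 2 mm.

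**Precision.** Losing one subject from one arm gives √(1/9 + 1/10) = 0.459, a rise of 2.7%. Losing one from each of two arms gives √(1/9 + 1/9) = 0.471, a rise of 5.4%.

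**Timing.** The protocol says: "Each subject in the OMT groups (i.e. OMT and OMT+BEMER) will receive treatment 3 times per week for a period of 3 weeks". That is 3 × 3 = 9 OMT sessions. An effect after any of the first eight would ordinarily precede the final questionnaire. Soreness 24 to 48 hours after the ninth might follow it and cost no data.

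**The case against.** The strongest reply is that the rule may never be used. The early stopping clause (Methodology III.A.3) reads "Any adverse effect, as determined by the attending licensed osteopathic physician. No adverse effects are anticipated", and III.B adds "Last year we have successfully utilized OMT and the BEMER therapy without any adverse effects in a prior study on low back pain". Nothing in the documents supports any particular non-zero rate, and the 22% figure needs both extremes together. All of that stands, and it is why the point is minor.

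A reader might infer that the rule flatters OMT by deleting the subjects who did badly on it. The documents do not support that. It would need post-OMT soreness to count as an adverse effect. Yet the protocol lists soreness as an expected risk while saying that no adverse effects are anticipated. The reading that reconciles the two is that its authors do not class soreness that way. Without that route, nothing places the losses in any one arm, and nothing shows whether removed subjects would have scored better or worse.

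A reader might also infer that follow-up after removal is forbidden. No sentence says so; none plans it. The consent form was not available, and withdrawal procedures could be described there.

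Two further objections stand in part. That a condition listed in II.C could arise from treatment is only a possibility, since the techniques are described as non-forceful. It justifies an exception in the wording and no more. Immediate removal is also a safety measure in a trial where students treat and the physician need not be in the room, so a fix should not make stopping discretionary. It need not: stopping treatment protects the subject, and a questionnaire adds no exposure.

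What remains is the rule as written. It covers any adverse effect, ends study participation rather than treatment, and has no planned outcome behind it.

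**Conclusion.** The point holds as a minor one. A stated rule excludes subjects after randomisation for a treatment-related reason and, in the text available, leaves those removed during treatment without planned post-treatment data. The number affected may be zero. The sign and size of any bias are unknown and the size is likely small: across the assumed ranges, 0 to 0.10 SD in an arm mean on average, in either direction. The conclusion about the text rests on the two planned assessment times and on the consent form adding nothing to them. The magnitudes rest on assumed rates and gaps. The case for acting is that the remedy is cheap and must be set before the data are collected.

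**What to change.** Keep the mandatory stop in III.B, but apply it to treatment. For example: *study treatment will be stopped immediately; the subject remains in the study, completes the NDI, SF-12 and VAS at the scheduled week-3 time, and is analysed in the assigned arm.*

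Add an exception to III.A so that a subject stopped for an adverse effect is not then removed for non-adherence. Add one to II.C for a listed condition that arises as an adverse effect of treatment.

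Leave Methodology III.A.3 unchanged unless the sponsor confirms that it applies to individual subjects. It sits under early stopping rules and may be meant for the whole trial, in which case rewriting it could remove the only trial-level stopping rule.

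The cost is an amendment approved by the IRB (Risks and Benefits I.C.2) and one questionnaire contact per affected subject, an expected 0 to 2 at the rates assumed above. The analysis will also include some subjects who had less than the full regimen. This change alone does not make the analysis fully by assignment, because III.A would still remove everyone who is non-adherent for other reasons.
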